5.0 Statistical Consideration

This is a randomized phase III trial to determine whether the use of Ibandronate significantly decreases the amount of bone loss in patients with BMT, compared to those in the control group. Patients will be equally randomized to control or treatment groups at baseline. All transplant patients will receive oral calcium 500 mg and vitamin D 400 IU twice daily throughout the trial.

The primary endpoint is the percent reduction in bone mineral density (BMD) of the lumbar spine, femoral neck, and total hip measured at 12 month relative to baseline, which we denote here as Diff_BMD. Assuming that the mean Diff_BMD is 12% decrease in the control group and is 0.1% in the treatment (Ibandronate) group, a maximum of 120 patients (60 patients per group)

will be needed in order to have an 80% power to detect this difference at a two-sided significance level of 0.05, assuming a common standard deviation of 0.23. Assuming a drop-out rate of 40% for the patients due to mortality and relapse in the first year, a maximum of 200 patients will be enrolled into the study. The total accrual period will be 20 months, with 10 patients enrolled per month.

Two interim analyses are planned for the primary endpoint of the percent reduction in BMD between baseline and 12 months, when 40 and 80 patients have been accrued into the study and followed for one year, respectively. A Lan-DeMets spending function with O'Brian-Fleming stopping boundaries has been assumed. The two-sided Z-score cut-off values for rejecting the null hypothesis are ± 3.71 and ± 2.51 for the two interim looks, respectively.

The change of BMD between baseline and 12 months will be summarized by treatment and control groups. Data will be transformed as appropriate to satisfy the normality assumption. A two-sample t-test on the transformed data or Wilcoxon rank-sum test will be performed to compare the two groups in terms of percent change of BMD from baseline to 12 months.

The change of BMD between baseline and 6 months will also be summarized and the percent change in BMD over time will be plotted for all patients and by treatment group, respectively. A linear mixed-effect model will be fit for the data set to investigate if there is a treatment effect at different time points and if the pattern of BMD change over time differs between two groups. Similar analysis will also be performed for graft rate, serum C-telopeptide (CTX) measured over time, as well as for cytokines associated with bone loss. The incidence rate of fracture will be estimated for each arm and will be compared between the two arms using Fisher's exact test.

The change of BMD between baseline and 12 months will also be summarized for patients with and without additional steroid treatment for GVHD after allogeneic bone marrow transplant separately. Wilcoxon rank sum test will be used to assess the difference in BMD change between patients with and without prolonged steroid and other immunosuppressant use for the treatment of GVHD, either in all patients or by treatment group. A multiple linear model will be fit for the BMD at 12 months, adjusting for baseline BMD and using steroid doses in GVHD, treatment as well as steroid use in GVHD and treatment interaction as predictors.

We will summarize the change of BMD between baseline and 12 months by disease type (i.e., hematological malignancies vs. hematological disorders). Wilcoxon rank sum test will be used to assess the difference in BMD change between patients with hematological malignancies and those with hematological disorders. A multiple linear model will be fit for the BMD at 12 months, using baseline BMD, disease type, treatment arm, as well as the interaction between disease type and treatment as covariates. The fitted model will help us address the question whether or not the treatment effect is similar in these two disease types.

Based on already published data (9) on risk of skeletal-related events (SRE) with ibandronate, modeling will be conducted to determine cost-effectiveness ratio of cost per SRE avoided, with sensitivity analysis. Costs will include the potential cost of treating for SREs and the potential cost of treating adverse events due to i.v. Ibandronate. One-way sensitivity analysis varying the key assumption (SRE relative risk reduction rate from 0% to 50% in 5% intervals) over the base case will be conducted to determine if it might impact the cost-effectiveness ratio.

Incremental Cost Effectiveness Ratio (ICER):

1.
$$\frac{(\text{Cost}_{\text{treatment}} - \text{Cost}_{\text{control}})}{(\# \text{SREs}_{\text{treatment}} - \# \text{SREs}_{\text{control}})}$$
2.
$$\frac{(\text{Cost}_{\text{treatment}} - \text{Cost}_{\text{control}})}{(\text{Months free of SREs}_{\text{treatment}} - \text{Months free of SREs}_{\text{control}})}$$

TreeAge Pro 2007 by TreeAge Software Inc., will be utilized for the cost-effectiveness calculations. The analysis will compute per-patient costs and benefits for the 12 month study period, following an intent-to-treat approach, and produce a cost-effectiveness ratio. The primary outcomes are incremental cost per percent of reduction in BMD and incremental cost per patient within one or two SD of normal BMD.

Two Incremental Cost Effectiveness Ratios (ICER) will be calculated:

1.
$$\frac{(\text{Cost}_{\text{treatment}} - \text{Cost}_{\text{control}})}{(\% \text{BMD reduction}_{\text{treatment}} - \% \text{BMD reduction}_{\text{control}})}$$
2.
$$\frac{(\text{Cost}_{\text{treatment}} - \text{Cost}_{\text{control}})}{(\# \text{Patients with normal BMD}_{\text{treatment}} - \# \text{Patients with normal BMD}_{\text{control}})}$$

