1.0 Objectives

This study plans to address the following hypotheses:

- 1.1 The addition of Ibandronate initiated immediately after the transplantation (21 to 60 days) will prevent bone loss in patients undergoing allogeneic bone marrow transplantation (BMT) with underlying hematologic malignancies or hematological disorders.
- 1.2 BMT patients who require prolonged steroid and other immunosuppressive treatment for Graft versus Host Diseases (GVHD) have a higher rate of bone loss, which can be prevented or attenuated by Ibandronate.

Specific objectives to test these hypotheses are:

a. Primary Objective:

1. To prospectively compare the bone mineral density changes of lumbar spine, femoral neck and total hip between patients randomly assigned to Ibandronate and control group over 12 months post bone marrow transplantation at the University of Texas MD Anderson Cancer Center.

b. Secondary Objectives:

1. To measure and compare the accumulated level of steroid used in both treatment and control groups.
2. To collect and compare the level of serum C-terminal telopeptide (CTX) in both treatment and control groups to monitor the bone turnover rate for the duration of the study.
3. To conduct a cost-effectiveness analysis of participating patients for both outcomes on bone mineral density (measured data) and skeletal-related events (modeled data).
4. To record incidence of bone fractures and the graft rate in both treatment and control groups.

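### Three BMD sites are primary, but alpha, power, sample size and interim cut-offs are set for one test, with no lead site, success rule or multiplicity control

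*Combined protocol and SAP*

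**What the plan says.** The primary objective in section 1.0 covers three skeletal sites without ranking them: "To prospectively compare the bone mineral density changes of lumbar spine, femoral neck and total hip between patients randomly assigned to Ibandronate and control group". Section 5.0 repeats the three sites as the endpoint, "The primary endpoint is the percent reduction in bone mineral density (BMD) of the lumbar spine, femoral neck, and total hip", and gives them a single symbol: "measured at 12 month relative to baseline, which we denote here as Diff_BMD".

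Every design quantity that follows is singular:

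- Effect: "Assuming that the mean Diff_BMD is 12% decrease in the control group and is 0.1% in the treatment (Ibandronate) group".
- Spread: "assuming a common standard deviation of 0.23".
- Operating characteristics: "80% power to detect this difference at a two-sided significance level of 0.05", with 60 evaluable patients per group, 120 in all, and 200 enrolled to allow for 40% drop-out.
- Interim looks: after 40 and 80 patients with one year of follow-up, from a Lan-DeMets spending function with O'Brien-Fleming boundaries and cut-offs of ±3.71 and ±2.51. No final cut-off is printed.
- Test: a t-test or Wilcoxon rank-sum test of percent change in BMD from baseline to 12 months. The site is not named.

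The rest of section 5.0 (mixed model, steroid and disease-type analyses, cost-effectiveness ratios) refers to BMD in the singular and does not settle the matter.

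**The concern.** One test has one success criterion. Three sites need a rule that turns three results into one conclusion, and the plan has none. A mixed outcome, such as a clear benefit at the spine and none at the femoral neck, could be reported as success or as failure, and the choice could be made with the results in view. The same gap affects the interim looks, because the plan does not say which site's statistic is compared with ±3.71 and ±2.51, or whether one site crossing would support an early efficacy claim. At stake are the two properties that the sample size paragraph promises, the 0.05 level and the 80% power.

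**Working it through.** **Inputs from section 5.0.** Difference 0.12 − 0.001 = 0.119; SD 0.23; 60 per arm; two-sided 0.05; power 80%; drop-out 40%; interim cut-offs 3.71 and 2.51.

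**Assumptions not in the document.** Equal correlation between the three sites' test statistics, shown from 0 to 0.95; a final cut-off of 1.993; information fractions of 1/3, 2/3 and 1 (40, 80 and 120 evaluable patients); for power, the planned effect and SD at every site.

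**1. The plan's own figure.** n per arm = 2(1.960 + 0.842)² × 0.23² / 0.119² = 58.6, so 59. With 60 per arm, the expected z is 0.119 / (0.23 × √(2/60)) = 2.83, and power is Φ(2.83 − 1.96) = 80.9% (80.3% by noncentral t). Enrolment is 120 / 0.6 = 200. The stated figures are those of one comparison.

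**2. One site uses all the alpha.** Simulating one site over three looks with 3.71, 2.51 and 1.993 gives 5.0% error and about 80% power. Nothing is left for two more sites.

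**3. Three sites.** With independent sites at a single look, any-site error is 1 − 0.95³ = 14.3% and all-three power is 0.809³ = 53%. Correlated cases were simulated as equicorrelated normal statistics:

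| Assumed correlation | Any-site error, three looks | All-three power, single look | Any-site power with Bonferroni, single look |
|---|---|---|---|
| 0 | 14.3% | 53% | 96% |
| 0.6 | 11.9% | 65% | 86% |
| 0.8 | 9.9% | 70% | 80.4% |
| 0.9 | 8.4% | 73% | 77% |
| 0.95 | 7.4% | 76% | 74% |

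Single-look any-site errors are almost the same (14.3%, 11.8% and 9.8% at 0, 0.6 and 0.8). The inflation therefore comes from the three sites, not from the repeated looks.

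**4. Bonferroni at 0.05/3.** The critical value is 2.394, so power at one named site is Φ(2.83 − 2.394) = 67%. Restoring 80% needs 2(2.394 + 0.842)² × 0.23² / 0.119² = 78.2, so 79 per arm. That is 158 evaluable and 158 / 0.6 = 263.3, so 264 enrolled.

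**5. Interim looks alone.** The chance of a false efficacy crossing is 1.2% for one site. For any of three sites it is 3.6%, 2.6% and 1.9% at correlations of 0, 0.8 and 0.95.

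**The case against.** The best defence is that Diff_BMD is one quantity. The single symbol, the single effect and SD, and the single BMD term in the cost-effectiveness ratios are all consistent with a combined measure, for which one test at 0.05 would suffice. This stands as a possible reading, but no average or composite of the sites is defined. It also means that the plan cannot be said to prescribe three separate tests at 0.05. The fault is an unresolved choice.

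Three stronger readings are tempting and are not supported:

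- **That false positives more than double.** This needs a correlation below about 0.78. The sites are measured in the same patients, so independence is the least plausible case, and at higher correlations the error is inflated but less than doubled.
- **That the plan must lose either its error control or its power.** A fixed testing order keeps both for the lead site. A Bonferroni rule under which any one site suffices also keeps power at or above 80% up to a correlation of about 0.8 if effects are equal across sites. Neither rule is in the plan.
- **That each site is tested at 0.05 at every look.** The cut-offs of ±3.71 and ±2.51 are far stricter than that, and the interim looks add at most about 0.1 percentage point to the any-site error.

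**Conclusion.** The gap is real and should be closed, since it concerns the primary analysis of a phase III trial. An any-site rule delivers a familywise error of about 7% to 14% instead of 5%. An all-site rule delivers about 53% to 76% power instead of 80%. Bonferroni at a single named site gives about 67%. Even at a correlation of 0.95, neither the any-site error nor the all-site power matches its stated value.

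That the rule is missing is certain from the text. The size of the consequence is conditional on the assumed correlation, on the assumed final cut-off of 1.993 and, for power, on the planned effect holding at every site. Section 2.0 itself says that loss is often worse at the femoral neck, so equal effects are a simplification.

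**What to change.** Before BMD is compared by arm, state one success rule in section 5.0 and apply it at the interim looks. A suitable rule is a fixed testing order:

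- Name one lead site. Femoral neck, then total hip, then lumbar spine is one possible order, since section 2.0 describes loss as often more severe at the femoral neck.
- Let only the lead site be compared with the interim boundaries for an efficacy stop.
- Test each later site only after every site before it has succeeded, against its own pre-stated group-sequential cut-offs. Print the final cut-off, and say which cut-off applies to the later sites if the trial stops early on the lead site.

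This holds familywise error at 5% whatever the correlation, and keeps about 80% power for the lead site with the planned 120 evaluable patients. It changes wording only.

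The cost is that later sites can be claimed only if earlier ones succeed. The chance of claiming all three remains about 53% to 76%. That is a single-look figure, and an early stop would lower it, because the later sites would then face a stricter cut-off on fewer patients. The order also matters: section 2.0 reports that pamidronate did not fully prevent loss at the hip and femoral neck, so the order above puts the spine behind the two sites where earlier treatment was incomplete. A defined composite, a co-primary rule or an any-site rule would also serve, if alpha and sample size are set to match.

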3. Other factors affecting bone metabolism will be measured which include 25(OH) Vit D and intact PTH levels at baseline (as part of pre-transplant workup, or prior to the enrollment) and at the end of the trial. If a patient was found to have vitamin D deficiency 3 months prior to the transplant and if a patient had been on weekly Ergocalciferol supplement, the patient will be eligible for this study and their vitamin D supplementation status will be considered as one of the randomization factor. Patient had prior Ergocalciferol supplement are randomized to either treatment or control group following the stratum 1 of the Randomization Scheme, Appendix F. Patients with no prior Ergocalciferol supplement are randomized according to the stratum 2 of the Randomization Scheme, Appendix F.

Sex hormones will be measured at the baseline (± 8 weeks) and the 12 months (± 8 weeks) (Testosterone or Estradiol, FSH and LH). Female patients who have documented laboratory values indicating postmenopausal state prior to the study entry will not be required to have new levels drawn. Female patients whose sex hormone levels showing menopausal state at baseline will not have repeat sex hormone study at the end of the trial. Serum for future research will also

be collected and banked at baseline and at 3, 6, 9, 12 months post transplant for measurements of cytokines and antibodies involved in the metabolism of the bone and the development of GVHD after the trial. Examples of future cytokine measurements may include: Osteoprotegrin (OPG), TNFa, Interleukin-6, GM-CSF, and IGF-1.

4. Incidence of fractures will be radiologically confirmed and compared between the two groups. Graft rate will be collected at 12 months for both groups and analyzed for statistical difference.

5. Data collection for the pharmaco-economic benefit model includes drug and administration costs via patient medical record databases and MDA Cost Accounting System.

Table 1: Summary of Treatment/study Plan

Assessments	1 month (21-45 days)	3 months	6 months	9 months	12 months
Medicine (IV)	x	x	x	x	
DEXA (bone mineral density)	x		x		x
Serum CTX	x	x	x		x
Routine lab : Ca, Mg, albumin, Cr, Alk phos	x	x	x	x	x
25 (OH)VitD, intact PTH, x					x
Sex Hormones Testosterone or Estradiol, FSH and LH (blinded and banked)	x				x
Serum collection for future x testing may include the following examples: Osteoprotegrin (OPG), TNFa, Interleukin-6, GM- CSF, IGF-1 (Banked)		x	x	x	x
Graft rate and Fracture rate					x

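### The primary 12-month BMD test is unadjusted and leaves out the 6-month scan, baseline BMD as a covariate and the randomisation stratum: the planned power is met, but precision is forgone and possible drop-out bias is not addressed

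*Combined protocol and SAP*

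**What the plan says.** Section 5.0 makes percent change in BMD from baseline to 12 months the primary endpoint. Data are to be transformed if normality requires it, and then "A two-sample t-test on the transformed data or Wilcoxon rank-sum test will be performed to compare the two groups". For this comparison the section names no covariate, stratum term, analysis set or missing-data method, and gives no rule for choosing between the two tests. Two interim analyses of the same endpoint are planned against fixed Z cut-offs of 3.71 and 2.51.

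The sample size calls for 60 evaluable patients per group and enrols 200: "Assuming a drop-out rate of 40% for the patients due to mortality and relapse in the first year".

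Section 4.0 schedules DEXA at baseline, 6 and 12 months in both groups. It also randomises within two strata by prior ergocalciferol use, where "their vitamin D supplementation status will be considered as one of the randomization factor". No planned analysis carries that stratum.

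After the primary test, Section 5.0 adds that "A linear mixed-effect model will be fit for the data set to investigate if there is a treatment effect at different time points". It also plans linear models of 12-month BMD that include baseline BMD and treatment, for the steroid and disease-type questions. None of these is called primary. Intent-to-treat is mentioned only for the cost-effectiveness analysis.

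**The concern.** A patient without a 12-month value contributes nothing to a two-sample test of 12-month change. If the planning assumption is right, the primary result rests on about 60 of 100 randomised patients per arm, and any 6-month scan from the others is set aside. Baseline BMD and the stratum, both known at randomisation, are not used to reduce residual variance.

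Two things are at stake. The first is precision that could be had from data already scheduled. The second is bias, if the patients who remain at 12 months differ in bone loss from those who leave, and differ in another way in one arm than in the other. The protocol itself ties treatment of GVHD to bone loss (Section 1.2 and Section 2.0), so selective loss is plausible. In addition, the open choice of transformation and of t-test or Wilcoxon means that the primary p-value, and the statistic compared with the interim boundaries, are not fixed in advance.

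**Working it through.** **Inputs from Section 5.0.** "two-sided significance level of 0.05"; "80% power to detect this difference"; "mean Diff_BMD is 12% decrease in the control group and is 0.1% in the treatment (Ibandronate) group", so the difference is 0.120 − 0.001 = 0.119; "common standard deviation of 0.23"; equal allocation; 40% drop-out.

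**The plan's own figure.** n per arm = 2(1.960 + 0.842)² × 0.23² / 0.119² = 58.6, so 59. The exact t-test calculation gives 79.6% power at 59 and 80.3% at 60, so 60 per arm reproduces. Enrolment is 120 / (1 − 0.40) = 200, which also reproduces. The normal approximation at 60 per arm gives 80.9%, and that is the reference for the power figures below.

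**Inputs not in the documents (assumed).** The correlation r of percent change with the covariates; the correlation ρ between 6- and 12-month change; and m, the number of the 40 drop-outs per arm who have a 6-month scan.

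**(a) Covariates only, 60 completers per arm.** Residual SD = 0.23 × √(1 − r²).

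| r | SD | Power | n per arm for 80% |
|---|---|---|---|
| 0.1 | 0.2288 | 81.3% | 59 |
| 0.3 | 0.2194 | 84.4% | 54 |
| 0.5 | 0.1992 | 90.5% | 44 |

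**(b) 6-month data only.** Variance factor = 1 − ρ² m / (60 + m); effective n = 60 / factor. The formula supposes that drop-out is unrelated to the 6-month value.

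| m | ρ | Factor | Effective n per arm | Power |
|---|---|---|---|---|
| 10 | 0.3 | 0.987 | 60.8 | 81.4% |
| 20 | 0.7 | 0.878 | 68.4 | 85.7% |
| 30 | 0.9 | 0.730 | 82.2 | 91.3% |

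**(c) Both.** With m = 20, ρ = 0.7 and r = 0.3, effective n = 60 / (0.878 × 0.91), and power is about 88.7%.

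**(d) Stratum alone.** If it explained 1% to 10% of the variance (assumed), the unadjusted standard error would be too large by 1/√0.99 to 1/√0.90, that is 0.5% to 5%. The error is conservative.

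**(e) Bias, by simulation.** 100 per arm, 4,000 runs, true 12-month difference 11.9 points. Assumed: mean 6-month loss of 8% in control and 0.1% on treatment, and 20% of patients with neither scan at random. Further drop-out before 12 months either rises with 6-month loss relative to the arm's own mean in both arms, or does so in the control arm only, with 25% at random on treatment.

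| Drop-out depends on 6-month loss | ρ | Completer difference | Estimate using 6-month data |
|---|---|---|---|
| in both arms, relative to own mean | 0.5 / 0.7 / 0.9 | 11.8 / 11.9 / 11.8 | 11.8 / 11.9 / 11.8 |
| in control only | 0.5 / 0.7 / 0.9 | 9.0 / 7.8 / 6.8 | 11.8 / 11.8 / 11.9 |

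The one-arm case costs 2.9, 4.1 and 5.1 points. The two estimates had similar spread (standard deviation 3.9 to 4.3 points for completers, 3.7 to 4.3 with 6-month data). When drop-out is selective, the gain is therefore mainly in bias, and the gain in (b) should not be added to it.

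An intermediate case is one common rule in both arms on absolute 6-month loss. An effective drug then makes drop-out unequal (for example 44% against 36%). With 40% drop-out overall, a 6-month effect of 6 to 11.9 points, ρ of 0.5 to 0.9 and a logistic slope of 0.5 to 2 per SD (all assumed), the completer difference lies between about 11.8 and 8.3 points. The bias is then between about 0.1 and 3.6 points.

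**The case against.** The strongest reply is that an unadjusted comparison of a change score is a valid randomised analysis, that 200 enrolled already pays for the expected loss, and that Section 5.0 does analyse the 6-month data, in a mixed model. On this view the dispute is only about which analysis is called primary. Much of that stands, and it rules out several stronger readings.

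- A reader might infer that the trial is underpowered. It is not: the stated power reproduces.
- A reader might infer that baseline BMD is discarded. It is the denominator of percent change and is absent only as a covariate. The planned models that adjust for it have raw 12-month BMD as outcome, where adjustment matters more.
- A reader might infer that a completer comparison is biased whenever drop-out relates to bone loss. It is biased only if selection on bone loss differs by arm. In the scenarios above the bias shrinks the effect and does not create one.
- A reader might infer that most drop-outs will have a 6-month scan. The documents do not say when drop-out occurs. They also do not connect death or relapse with GVHD or steroid use; that step is an inference.
- A reader might infer that the mixed model cures the problem. It protects only if data are missing at random given the observed BMD, and it implicitly assigns a 12-month BMD to patients who died.

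The reply does not remove the point. Forty percent loss is expected, the primary test has no missing-data plan or stated analysis set, and a more informative model is already in the plan but not used for the primary question.

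**Conclusion.** The point holds as an improvement in method, not as an error in the sample size or an invalid test. At the same enrolment, power would be about 81% to 91% from either source of information alone, against the planned 80%. If the correlations are low, the gain is a point or less. Bias ranges from negligible to about 3 to 5 of the 11.9 points, the upper part only where drop-out follows 6-month loss in one arm. All these ranges rest on assumed correlations, scan counts and drop-out mechanisms. That the test is in effect a completer analysis is inferred from the absence of any stated analysis set or imputation, and the 40% is itself a planning assumption. The stratum omission is minor and conservative.

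**What to change.** - Name one primary analysis: the mixed model of Section 5.0 on percent change (or log BMD ratio) at 6 and 12 months, with treatment, visit, treatment-by-visit, baseline BMD and prior-ergocalciferol stratum. The model as now described names neither of the last two. The primary contrast is the 12-month treatment difference.
- Define the analysis set, for example all randomised patients with a baseline and at least one later scan.
- Use the same model-based statistic at both interim looks.
- Keep one unadjusted test, t-test or Wilcoxon, with its transformation fixed in advance, as a sensitivity analysis.
- State the estimand for patients who die or relapse, and add a delta-adjusted missing-not-at-random sensitivity analysis.

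The cost is a change to the text of Section 5.0, a little more analysis work, and interim statistics computed from the model. All the data are already scheduled for collection.

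### Fracture is compared by Fisher's exact test, which ignores follow-up time, with no rule for the 40% expected to drop out in the first year

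*Combined protocol and SAP*

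**What the plan says.** Fracture is the fourth secondary objective (section 1.0): "To record incidence of bone fractures and the graft rate in both treatment and control groups". Section 4.0, item 4, adds: "Incidence of fractures will be radiologically confirmed and compared between the two groups". That sentence gives no collection time; the next one ties only the graft rate to 12 months. Table 1 in section 4.0 has a row "Graft rate and Fracture rate" with a single mark, in the 12-month column.

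Section 5.0 gives the analysis: "The incidence rate of fracture will be estimated for each arm and will be compared between the two arms", by Fisher's exact test. The same section sets the sample size for bone mineral density (BMD) and inflates it: "Assuming a drop-out rate of 40% for the patients due to mortality and relapse in the first year".

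The documents do not state the fracture denominator or analysis set, whether fractures before death or relapse are counted, how patients without a 12-month assessment are classified, or any time-to-event method. An intent-to-treat approach is named only for the cost-effectiveness analysis.

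**The concern.** The plan promises an incidence rate but tests a two-by-two table. Each patient enters that table as yes or no, or is left out. For a patient who leaves at month 4 without a fracture, neither entry uses what is known, namely four fracture-free months and nothing after.

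On the plan's own figure this affects up to 80 of 200 patients, and the choice of denominator changes the estimate. Analysing completers discards fractures seen before drop-out. Analysing everyone codes living patients who were lost as fracture-free for a period in which nobody looked.

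Fracture is secondary, but section 5.4 presents later fracture prevention as the reason why bone loss matters. Sections 2.0 and 5.4 also say that bone loss is fastest in the first three to six months, so events from early follow-up should not be dropped by default.

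**Working it through.** **Inputs from the documents (section 5.0).** 120 evaluable patients, 60 per group; 40% drop-out; 200 enrolled; 1:1 allocation; Fisher's exact test.

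**The plan's own figure.** 120 / (1 − 0.40) = 200, which reproduces exactly. So 200 − 120 = 80 patients are expected to drop out before the 12-month assessment.

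**Assumptions.** The documents give no fracture rate, so I take a 12-month risk F (absent drop-out) of 5%, 10% or 20%. Fracture and drop-out hazards are constant and independent, with d = 0.40.

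**Formulas.**
- λ = −ln(1 − F) and h = −ln(1 − d) = 0.511.
- Fractures under observation, per patient randomised: C = λ/(λ + h) × [1 − (1 − F)(1 − d)].
- Fractures in completers: (1 − d)F. Share lost if only completers are analysed: 1 − (1 − d)F/C.
- If early fractures are counted but other drop-outs are excluded, the reading is C/[C + (1 − F)(1 − d)].

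**Worked case, F = 10%.** λ = 0.105. C = 0.105/0.616 × (1 − 0.54) = 0.0787. Completer fractures = 0.060. Lost = 0.0187, and 0.0187/0.0787 = 23.7%. Third reading = 0.0787/(0.0787 + 0.54) = 12.7%.

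| Assumed F | Completers only | Fractures lost by using completers only | All randomised | Early fractures in, other drop-outs out |
|---|---|---|---|---|
| 5% | 5.0% | 0.9 per 100 (23.5%) | 3.9% | 6.4% |
| 10% | 10.0% | 1.9 per 100 (23.7%) | 7.9% | 12.7% |
| 20% | 20.0% | 3.8 per 100 (24.1%) | 15.8% | 24.8% |

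Follow-up time agrees. 200 × 0.40/0.511 = 156.6 patient-years, of which 156.6 − 120 = 36.6 (23%) come from patients who do not reach 12 months.

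**Deaths versus living losses.** C is also the cumulative incidence of fracture when the other exit is death. The error in the all-randomised reading therefore depends on the mix of losses, which the plan does not give. For F = 10% the reading is 7.9% in every case, but the target (cumulative incidence with death competing and living patients followed) moves:
- all losses living: 10.0%;
- half the drop-out hazard is death (h/2 = 0.255): 0.105/0.361 × (1 − 0.9 × √0.6) = 8.8%;
- all losses deaths: 7.9%, so no error.

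**Drop-out related to fracture risk.** Assume drop-out times are uniform over the year and drop-outs have twice the completers' fracture hazard. Drop-outs then have 3.93 fractures per 100 randomised against 6.0 in completers (F = 10%). The share lost is 3.93/9.93 = 40%.

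**Effect on the comparison.**
- *Equal 40% loss, equal hazards.* Both arms read 7.9%, with no spurious difference.
- *Power for an assumed 10% versus 5%, two-sided 0.05.* 19% with 100 per arm and no drop-out; 9% with 60 completers per arm; 14% with all randomised.
- *Unequal loss of living patients (assumed 30% versus 50%), equal 10% risk.* The arms read 0.105/0.462 × 0.37 = 8.4% and 0.105/0.799 × 0.55 = 7.3%, a spurious risk ratio of 0.86. With 100 per arm, Fisher's test would reject 3.4% of the time, so the damage is to the estimate rather than a surplus of false positives.

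**The case against.** The other side has a good case, and much of it stands.

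- *A reader might infer that Fisher's test is invalid because it assumes equal follow-up.* It does not. Under randomisation, with loss equal across arms and unrelated to fracture, it keeps its type I error even though individual follow-up varies.
- *A reader might infer that the estimate is wrong whichever denominator is used.* That is too strong. The completer proportion is unbiased for the risk absent drop-out if drop-out is unrelated to fracture, although it wastes events. For deaths, the all-randomised proportion is the cumulative incidence one would want.
- *A reader might infer that 40% will be unobserved for fracture.* The 40% was set for the 12-month BMD endpoint, and nothing says that fracture recording stops at relapse. The 12-month timing of fracture rests on one table mark, which could denote a cumulative count. Even so, a yes/no test must code living drop-outs without a fracture as fracture-free or exclude them.
- *A reader might infer that trial fracture counts feed the cost per skeletal-related event avoided.* They do not: sections 1.0 and 5.0 say those events are modelled, from published data.
- *Unequal loss by arm is not documented.* The plan gives one drop-out figure. No placebo is described and only the treated arm has infusions, so unequal loss is possible, but nothing predicts it.
- *Fracture is an unpowered secondary endpoint, and an exact test suits sparse events.* True. This lowers the priority and is a reason to keep Fisher's test in a supporting role.

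**Conclusion.** The point holds in limited form. The plan names a test that ignores follow-up time and sets no rule for patients who drop out.

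If only completers are analysed, about 24% of fractures under observation are lost, assuming constant independent hazards, and about 40% if drop-outs carry twice the fracture hazard. If all randomised patients are analysed, an assumed 10% risk reads 7.9%. The correct value lies between 7.9% and 10.0%, depending on how many of the losses are deaths.

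With equal loss unrelated to fracture, the consequence is a distorted estimate and reduced power, not a false-positive problem. The comparison between arms is biased only if loss of living patients differs by arm or is related to fracture risk, and the documents establish neither. All fracture rates here are assumptions. The change is worth making because it is cheap, but it concerns a secondary endpoint and does not touch the primary analysis.

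**What to change.** - Record the date of every radiologically confirmed fracture in all randomised patients, from randomisation to 12 months, death or last contact, whichever comes first. Include fractures after relapse where the patient is still followed.
- State that the fracture analysis set is all randomised patients.
- Report 12-month cumulative incidence by arm, with death as a competing event and living losses censored at last contact. Compare the arms with Gray's test.
- Keep Fisher's exact test as a sensitivity analysis, with its denominator stated, because events may be sparse and Gray's test is asymptotic.
- Report the numbers of deaths and of living losses by arm.

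The cost is one date field, a few sentences in section 5.0 and slightly more analysis. The change will not make fracture a powered endpoint. Censoring still assumes that living losses are unrelated to fracture risk, which is why fracture follow-up after relapse matters.
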